4.5.2.2 Unsolicited Adverse Events

All intercurrent diseases reported when the investigator actively inquires the subject will be documented as unsolicited adverse events. Unsolicited AEs will be assessed and documented from ICF signature through EAP, and if ongoing at that time followed until resolution or until the subject's last trial visit, at the latest. SAEs and AESIs will be collected through the end of the trial, including during the FU period, and followed-up until resolution or achievement of stable clinical conditions.

Relationship of the trial vaccine to the AE is assessed by the investigator using the categories "none," "unlikely," "possible," "probable," and "definite." An AE assessed as possibly, probably, or definitely related will be counted as a related AE for the purpose of reporting. AEs categorized as none or unlikely for causality will not be considered related to trial vaccination. AEs missing a relationship will not have a causality imputed.

Unsolicited AEs are graded based on the *Toxicity Grading Scale for Healthy Adult and Adolescent Volunteers Enrolled in Preventive Vaccine Clinical Trials* ([FDA, 2007](#)). The maximum toxicity grade over the duration of the AE will be reported in the case report form. If a subject has multiple AEs within the same PT, the highest toxicity grade will be used for subject-level summaries. Grading will be based on the descriptions listed in [Table 5](#).

Table 5 Adverse Event Grading

Grade	Definition
Grade 1	An AE which is easily tolerated by the subject, causing minimal discomfort and not interfering with daily activities.
Grade 2	An AE which is sufficiently discomforting to interfere with daily activities, but does not require medical intervention (non-narcotic pain reliever or other nonprescription medication are not considered "medical intervention" for this purpose).
Grade 3	An AE which prevents daily activities and which requires medical intervention (non-narcotic pain reliever or other nonprescription medication are not considered "medical intervention" for this purpose)
Grade 4	Life-threatening, or disabling.

Analysis

The secondary estimand analyses for SAEs, AESIs, and related \geq Grade 3 AEs within 8 days after vaccination are described in [Section 4.3](#).

In general, AEs will be summarized by SOC, PT, and group for the Safety Analysis Set in the Active Trial Period. AEs occurring after the Active Trial Period during the FU period will be included in the AE listings. AEs occurring between ICF signature and first vaccination will be

considered Baseline Signs and Symptoms and will be reported similarly to medical history events.

For Group 1, summaries will also be included by period for Vaccination Period 1, Vaccination Period 2, and the overall Active Trial Period. For the overall Active Trial Period, event counts will include events from both vaccination periods in the case a subject experiences the same event multiple times.

Groups 2 and 3 will be summarized for the Active Trial Period, separately from Group 1.

An overall summary of solicited and unsolicited AEs including subject counts, event counts, percentages (of subjects only) will be created for the following event categories:

Solicited and Unsolicited AEs

- All AEs
- SAEs
- AEs Leading to Withdrawal
- Fatal AEs

Solicited AEs

- Local AEs
 - \geq Grade 3
 - Leading to Deferral or Discontinuation of Vaccine
 - SAEs
- General AEs
 - \geq Grade 3
 - Related
 - Related \geq Grade 3
 - Leading to Deferral or Discontinuation of Vaccine
 - SAEs

Unsolicited AEs

- All AEs
 - Related
 - \geq Grade 3
 - Related \geq Grade 3

- Leading to Withdrawal
- SAEs
 - Within 8 Days After Vaccination
 - Within 29 Days after Vaccination*
 - Related SAEs
 - Fatal
- AESIs
 - Within 8 Days After Vaccination
 - Within 29 Days after Vaccination*
 - Related AESIs
- Related AEs \geq Grade 3
 - Within 8 Days After Vaccination
 - Within 29 Days after Vaccination*

*Within 29 days summaries includes through the day prior to second vaccination for Group 1 Vaccination Period 1, or from the last/single booster vaccination through the end of the Active Trial Period for all groups. The window for the end of the Active Trial Period visit is 28-35 days post last/single booster vaccination.

Summary tables for unsolicited AEs by SOC and PT will be presented including subject and event counts and percentages (of subjects only) for the Active Trial Period:

- AEs
- Related AEs
- AEs \geq Grade 3
- Related AEs \geq Grade 3
 - Related AEs \geq Grade 3 Occurring within 8 Days of any Vaccination
 - Related AEs \geq Grade 3 Occurring within 29 Days of any Vaccination*
- Non-serious AEs in $> 5\%$ of Subjects
- SAEs
- Related SAEs
 - Related SAEs Occurring within 8 Days of any Vaccination
 - Related SAEs Occurring within 29 Days of any Vaccination*
- AESIs

- Related AESIs
 - Related AESIs Occurring within 8 Days of any Vaccination
 - Related AESIs Occurring within 29 Days of any Vaccination*
- AEs Leading to Discontinuation of Active Trial Period

*Within 29 days summaries includes through the day prior to second vaccination for Group 1 Vaccination Period 1, or from the last/single booster vaccination through the end of the Active Trial Period for all groups. The window for the end of the Active Trial Period visit is 28-35 days post last/single booster vaccination.

Tables summarized by SOC and PT will be sorted in order of descending incidence of SOCs in the overall column, and descending order of incidence of PTs within the SOCs. For subject level frequencies and percentages, subjects experiencing an event more than once will be counted only once within SOC and PT, however all events will be counted in the event column.

All AEs will be listed by group, subject, onset date, SOC, and PT. Separate listings will be created for SAEs, AESIs, AEs \geq Grade 3, and AEs leading to discontinuation of the Active Trial Period. Listings will include any AEs collected during the FU period.

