8.12 Unsolicited AEs

All intercurrent diseases reported when the investigator actively inquires the subject will be documented and all required details (e.g., start and stop date, intensity) will be assessed. Unsolicited AEs will be reported in the subject's medical record and respective section of the eCRF (requirements for screen failures see [Section 12.1](#)).

Unsolicited AEs will be assessed and documented from ICF signature through EAP, and if ongoing at that time followed until resolution or until the subject's last trial visit, at the latest. SAEs and AESIs will be collected through the end of the trial, including during the FU period.

SAEs and AESIs will be assessed and documented at all trial visits. (S)AEs would only be considered as AESIs once subject has received first vaccination. SAEs and AESIs will be followed-up until resolution or achievement of stable clinical conditions.

Assessment of Intensity

For all unsolicited AEs not represented in the Toxicity Grading Scale for Healthy Adult and Adolescent Volunteers Enrolled in Preventive Vaccine Clinical Trials ([FDA, 2007](#)), the maximum intensity will be based on the following descriptions:

- Grade 1** An AE which is easily tolerated by the subject, causing minimal discomfort and not interfering with daily activities.
- Grade 2** An AE which is sufficiently discomforting to interfere with daily activities, but does not require medical intervention (non-narcotic pain reliever or other nonprescription medication are not considered “medical intervention” for this purpose).
- Grade 3** An AE which prevents daily activities and which requires medical intervention (non-narcotic pain reliever or other nonprescription medication are not considered “medical intervention” for this purpose)
- Grade 4** Life-threatening, or disabling.

Assessment of Causality

The relationship between the occurrence of an AE and the IMP will be assessed using the categories presented below. For expedited reporting and all other purposes, the categories “none” and “unlikely” will represent no evidence or argument to suggest a causal relationship, while “possible”, “probable” and “definite” will be seen to convey that there is evidence or argument to suggest a causal relationship. To ensure reporting, all AEs without a causality assessment from the investigator will preliminarily be classified as “possible”.

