In terms of binary causality assessments unlikely and not related in clinical trials is lumped to “not related” whereas other causality assessments as per below are lumped to “related”.

- Not related** The time interval between administration of the IMP and the occurrence or worsening of the AE rules out a relationship, and/or alternative cause is established and there is no evidence of a (concomitant) causal connection with or worsening caused by the IMP.

Unlikely	The time interval between administration of the IMP and the occurrence or worsening of the AE makes a causal relationship unlikely, and/or the known effects of the IMP or substance class provide no indication of a (concomitant) causal connection with or worsening caused by the IMP and there is another cause which serves as an adequate explanation, and/or although the known effects of the IMP or substance class make it possible to derive a plausible causal chain with regard to a (concomitant) causal connection or worsening, however, another cause is considerably more likely, and/or another cause of the AE has been identified and a (concomitant) causal connection with or worsening caused by the IMP is unlikely.
Possible	A plausible causal chain with regard to a (concomitant) causal connection with / worsening of the AE can be derived from the pharmacological properties of the IMP or substance class. However, other approximately equally likely causes are known, or although the pharmacological properties of the IMP or substance class provide no indication of a (concomitant) causal connection with / worsening of the AE, there is no other known cause which provides an adequate explanation.
Probable	The pharmacological properties of the IMP or substance class, and/or the course of the AE after discontinuation of the IMP and possible subsequent re-exposure, and/or specific findings (e.g., positive allergy test or antibodies against the IMP / metabolites) suggest a (concomitant) causal connection with / worsening of the AE resulting from the IMP, however another cause cannot completely be ruled out.

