4.3 Secondary Estimand Analyses

4.3.1.1 Definition of Endpoints

Percent of subjects reporting any SAE or AESI, as well as \geq Grade 3 AEs assessed as related to trial vaccine within 8 days after vaccination.

The second intercurrent event, discontinuation due to AEs from either the second vaccination (Group 1) or the trial (all groups), is relevant for this estimand. If it is confirmed by the investigator that the subject discontinues the trial within 8 days after vaccination due to AEs, the subject is considered having a related SAE/AESI/Grade 3 or higher AE regardless of the seriousness, severity, or causality of the AE for which the subject discontinued. This is consistent with the “composite” strategy.

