4.3.1.2 Main Analytical Approach

For the Safety Analysis Set, the percent of subjects reporting any related SAE or AESI, as well as subjects reporting any related \geq Grade 3 AE within 8 days after any vaccination will be summarized, and the 95% CI will be calculated using the Clopper-Pearson method. For Group 1, this analysis will be performed by vaccination period and for the overall Active Trial Period.

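### An AE whose causality is still blank at analysis stays out of the related 8-day endpoints under SAP 4.5.2.2, although protocol 8.12 provisionally treats it as related

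*SAP*

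**What the plan says.** Protocol 8.12 (Assessment of Causality) has a default for a missing assessment: "To ensure reporting, all AEs without a causality assessment from the investigator will preliminarily be classified as" *possible*. Its binary rule puts *not related* and *unlikely* on one side, while "other causality assessments as per below are lumped to" *related*. *Possible* therefore falls on the related side.

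SAP 4.5.2.2 uses the same split for assessed events: "An AE assessed as possibly, probably, or definitely related will be counted as a related AE for the purpose of reporting". For unassessed events it says: "AEs missing a relationship will not have a causality imputed".

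Both secondary endpoints need the related label. SAP 4.3.1.2 takes "For the Safety Analysis Set, the percent of subjects reporting any related SAE or AESI", and likewise any related Grade 3 or higher AE, within 8 days of any vaccination, with Clopper-Pearson 95% intervals. SAP 4.3 has no rule of its own for blank causality. The composite rule in SAP 4.3.1.1 counts a subject who leaves the trial because of AEs within 8 days "regardless of the seriousness, severity, or causality of the AE for which the subject discontinued".

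SAP section 1 says that changes to the protocol's planned analyses are described in 4.7. That section lists two: the restriction of the primary analysis to Groups 2 and 3, and an added 6-fold response threshold. Missing causality is not mentioned.

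**The concern.** The protocol resolves a missing assessment towards related, and the SAP leaves it unresolved. An event with no category does not meet the SAP's definition of related, so it cannot enter the numerator of either endpoint. Compared with the protocol's default, this can only lower the related rate. In a safety endpoint that is the less cautious direction.

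The other planned outputs compensate only in part. In the SAP 4.5.2.2 overall summary, SAEs and AESIs each have a row "Within 8 Days After Vaccination" that ignores causality. Unsolicited Grade 3 or higher AEs have an 8-day row for related events only. Regardless of cause, they appear in tables for the whole Active Trial Period and in the listings ("All AEs will be listed by group, subject, onset date, SOC, and PT"). A blank-causality Grade 3 event within 8 days would be on record, but in no 8-day count.

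**Working it through.** **Following one event through the rules.** Take an unsolicited Grade 3 AE on Day 4 with the causality field empty.

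1. Protocol 8.12: provisionally *possible*, hence related.
2. If *possible* is written to the database, SAP 4.5.2.2 also counts it as related. There is no difference.
3. If the field is blank in the analysis data, SAP 4.5.2.2 assigns no category. The event is not possible, probable or definite, so it is not counted.
4. If the subject left the trial because of AEs within 8 days, the composite rule counts the subject anyway. The treatment-policy sensitivity analysis (SAP 4.3.1.3) would drop that subject again, unless the AE that led to discontinuation itself qualifies.
5. If the subject has another qualifying event in the window, the subject already counts and the blank changes nothing.

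Solicited local AEs are related by definition (protocol 8.14, SAP 4.5.2.1), so their causality cannot be blank in effect. Solicited general AEs use the same causality categories as unsolicited ones. The SAP's sentence stands in the unsolicited section, and the SAP does not say how a blank is handled for them.

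**Size.** The plan states no expected rate or precision for these endpoints, so there is no figure to reproduce. Its precision calculations concern titers and have no bearing here.

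Inputs: n = 30 in Group 1 and n = 90 in each of Groups 2 and 3 (SAP section 6). The number of affected subjects is an assumption, shown from 0 to 2.

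Change per affected subject = 1/n: 1/30 = 3.33 points; 1/90 = 1.11 points.

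Clopper-Pearson 95% limits for x of n: the lower limit is the 0.025 quantile of Beta(x, n − x + 1), or 0 when x = 0. The upper limit is the 0.975 quantile of Beta(x + 1, n − x).

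| Subjects counted | n = 30 | n = 90 |
|---|---|---|
| 0 | 0% (0 to 11.57) | 0% (0 to 4.02) |
| 1 | 3.33% (0.08 to 17.22) | 1.11% (0.03 to 6.04) |
| 2 | 6.67% (0.82 to 22.07) | 2.22% (0.27 to 7.80) |
| 3 | 10.00% (2.11 to 26.53) | 3.33% (0.69 to 9.43) |

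If no other subject qualifies, one affected subject is the step from row 0 to row 1, and two are the step from row 0 to row 2. If two subjects already count for other reasons, one more is the step from row 2 to row 3: the same 1/n, but no longer the difference between none and some. With no affected subjects there is no step.

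**Time to resolve blanks.** SAP 4.6 runs the Groups 2 and 3 analysis after the EAP visit at V1 +28-35, on data cleaned through that visit. Day 8 is V1 +7, so for a subject who completes the active phase the window closed at least 28 − 7 = 21 days earlier.

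**The case against.** The strongest reply is that the two texts need not conflict. The protocol's default is labelled preliminary and is there to make sure that events get reported. It may be an interim status until the investigator decides, while the SAP speaks of what is still missing at analysis. This reading is open and makes the point conditional. It does not remove it. Protocol 8.12 says its grouping of categories serves expedited reporting and every other purpose, and neither document says what happens if the provisional status is never replaced. By writing a rule for a missing relationship, the SAP also allows that blanks may remain.

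A second reply is that the endpoints concern events *assessed* as related, and an event that nobody assessed does not literally qualify. That is fair, and it is why the as-recorded result should stay visible.

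A third is that blanks should be rare. Protocol 12.1 requires complete eCRFs to which the investigator attests, data are cleaned through the EAP visit, and SAP 4.6 promises to document any later change in the data. This stands and keeps the priority low.

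Some stronger inferences are tempting, and the documents do not support them:

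- *The SAP declares missing causality to mean unrelated.* It does not. Exclusion follows from its definition of related.
- *Such events vanish from the report.* They do not. They remain in the tables and listings that ignore causality.
- *The Grade 3 endpoint as a whole is exposed.* Severe local reactions count automatically, and a subject who has one is unaffected by a blank on another event.
- *The SAP contradicts its own worst-case rule.* The rule in SAP 4.1.3 covers partial or missing dates and assigns events to study periods. It states no principle about causality.

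**Conclusion.** The protocol and SAP handle a missing causality assessment differently, and SAP 4.7 does not declare the difference. If blanks remain in the analysis data, the SAP's rule can only lower the two related 8-day rates relative to the protocol's default, by up to 3.3 points in Group 1 or 1.1 points in Group 2 or 3 for each affected subject. That size assumes that the subject has no other qualifying event and did not leave the trial because of AEs within 8 days. If no blanks survive cleaning, the effect is zero. The documents give no basis for predicting how many will.

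The endpoints are descriptive and no hypothesis is tested, so this is a minor point. It is worth settling because related events may be few, and one subject can then decide whether a table reads none or one.

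A reader might also infer that Group 1's first memory aid, which can be collected at V1 +5-7 although it covers 8 days, adds to the under-count. The documents do not establish this: nothing in them says that recording stops at collection. The visit window and the diary period should be reconciled as a separate matter, which adds no weight here.

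**What to change.** In SAP 4.3 and 4.5.2.2, state that a post-vaccination AE with causality still missing at the data cut is counted as related, in line with protocol 8.12. Beside it, show the as-recorded result, with blanks not counted, as a sensitivity line. Report the number of AEs with missing causality by group, and list the handling in SAP 4.7. It would help for the same sentence to say whether it also covers solicited general AEs.

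The cost is one or two sentences and one extra table line. The drawback is that some blanks would have been assessed as unrelated, so the related rate may read slightly high; the as-recorded line shows by how much. If no blanks remain, the two lines agree and the reported count of zero settles the question.

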Secondary Endpoints	
Subjects reporting any SAEs or AESIs assessed as related to trial vaccine within 8 days after vaccination.
 
Subjects reporting any Grade 3 or higher AEs assessed as related to trial vaccine within 8 days after vaccination.

Exploratory Endpoints	
Group 1 (seronegative subjects): SARS-CoV-2 neutralizing antibody titers at 2 and 4 weeks post-prime vaccination and 1, 4, and 13 weeks post-boost vaccination.
 
SARS-CoV-2 total antibody titers at all serum sampling time points.
 
Groups 2 and 3 (seropositive subjects): SARS-CoV-2 neutralizing antibody titers at 1 week, 4 weeks, 3 months, 6 months, 1 year and 2 years after vaccination.
 
SARS-CoV-2 total antibody titers at all serum sampling timepoints.

	
Groups 1, 2 and 3 (all subjects): Cellular immune response, e.g., by Interferon-γ / Interleukin-4 ELISPOT, at 1 week after the last vaccination, i.e., after the second vaccination in initially seronegative subjects and after the single boost vaccination in initially seropositive subjects.
 
SARS-CoV-2 neutralizing antibody titers against variant strains circulating at the time of analysis at 2 weeks after last vaccination.

Safety Endpoints	
Subjects reporting any SAE or AESI, regardless of relationship, within 29 days after vaccination.
 
Subjects reporting any Grade 3 or higher AEs assessed as related to trial vaccine within 29 days after vaccination.
 
Subjects reporting solicited local AEs within 8 days after vaccination.
 
Subjects reporting solicited general AEs within 8 days after vaccination.

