
Secondary
 
To assess the safety and tolerability of the ABNCoV2 vaccine in adult seropositive and seronegative subjects.
	
Secondary:
 
 Subjects reporting any Serious Adverse Events (SAEs) or Adverse Events of Special Interest (AESIs) assessed as related to trial vaccine within 8 days after vaccination Subjects reporting any Grade 3 or higher Adverse Events (AEs) assessed as related to trial vaccine within 8 days after vaccination For the primary analysis of these endpoints, if the investigator confirms the subject discontinues the trial within 8 days after vaccination due to AEs, the subject is considered having a related SAE/AESI/Grade 3 or higher AE regardless of the seriousness, severity, or causality of the AE for which the subject discontinued. This is consistent with the “composite” strategy. 
Sensitivity Analyses:
 
 Subjects who discontinue the trial within 8 days after vaccination due to AE will be analyzed using the “treatment policy” strategy to handle the intercurrent event, where the subject will not be considered having a related SAE/AESI/Grade 3 or higher AE assessed as related to trial vaccine, unless the specified AE leading to discontinuation meets one or more of these categories.

Objectives	Endpoints
	
Supportive Endpoints:
 
 Subjects reporting any SAE or AESI, regardless of relationship, within 29 days after vaccination. Subjects reporting any Grade 3 or higher AEs assessed as related to trial vaccine within 29 days after vaccination. Subjects reporting solicited local AEs within 8 days after vaccination. Subjects reporting solicited general AEs within 8 days after vaccination.

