4.1.3 Study Periods and Windowing

The following study periods are defined for this trial:

Screening Period: The period from the subject's signing of informed consent to the trial through the date and time of first vaccination. AEs starting during this period are considered Baseline Signs and Symptoms.

Active Trial Period: The period from the first vaccination up to and including week 4 (28-35 days) after receiving their vaccination. A visit at the end of the Active Trial Period is scheduled per protocol. In the event of early withdrawal of a subject from the trial during the Active Trial Period, the EAP visit may occur prior to the 28-35 days post-last vaccination window. For the purpose of safety analyses, any safety information collected within 35 days of their vaccination received will be included in summaries of the Active Trial Period.

FU Period: The period from the EAP visit through the final follow up visit. Subjects have 3 FU visits at 4, 9 and 22 weeks after the scheduled EAP visit (Weeks 8, 13 and 26). Subjects may withdraw from treatment early but continue into the FU Period.

For assigning prior and concomitant medications, those ending prior to the first vaccination are considered prior medications. All other medications are considered concomitant medications.

For AEs and medications with partial or missing start and/or stop dates, the “worst case” should be applied to be conservative. Therefore, the following rules will apply:

AEs

- If start date is partial and any portion (i.e., year or month and year) would confirm the AE was prior to first vaccination, the AE will be considered a Baseline Sign or Symptom.
- If the start date is completely missing and the end date, or any portion of a partial end date, confirms the AE ended prior to first vaccination, the AE will be considered a Baseline Sign or Symptom.
- Otherwise, the AE will be considered as belonging to the Active Trial Period.

Medications

- If the end date is partial, and any portion confirms the medication was ended prior to first vaccination, the medication will be considered a Prior Medication.
- Otherwise, the medication will be considered a Concomitant Medication.

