Per protocol, all visits are to occur within the specified window in the Trial Schedules ([Appendix 2](#) and [Appendix 3](#)). For the purpose of the primary estimand, rules for inclusion into the Immunogenicity Analysis Set will ensure immunogenicity samples taken too far out of window will not be included for analysis. For sensitivity analyses, immunogenicity samples taken out of window will be handled as described in Section [4.2.3.1](#).

In general, safety analyses will be performed for the Active Trial Period, accounting for any observations between the first vaccination and the EAP visit, inclusive of the EAP visit and any unscheduled visits during this period. In the event of early discontinuation from the Active Trial Period (i.e., EAP occurs prior to one month post last vaccination), safety results through 35 days (upper limit of the EAP visit window) post-last vaccination will be analyzed along with the Active Trial Period summaries. For Group 1, safety summaries will be performed by vaccination as well as for the overall Active Trial Period. Nominal visits will be used for the by-visit summaries, with the worst/highest toxicity grade value presented for the visit in the case of multiple reported observations.

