4.5.2.1 Solicited Adverse Events

Solicited AEs are defined as all symptoms specifically listed in the memory aid provided to the subjects following each vaccination. After vaccination, the subjects are requested to monitor and record local symptoms (i.e., erythema, swelling, induration, pruritus and pain at the injection site) as well as general symptoms (i.e., body temperature increase/pyrexia, headache, chills, myalgia, nausea and fatigue) in the memory aid daily for the day of vaccination and the following 7 days (Days 1 to 8 following vaccination, 8-day period). If symptoms persist at Day 8, daily symptoms and temperatures will be documented each day until resolved. Solicited AEs that meet the criteria for SAEs will be documented in the AE case report form as well as the memory aids.

As Group 1 receives 2 vaccinations, summaries will be presented by vaccination period and for the overall Active Trial Period. For Groups 2 and 3, there will be a single summary for the Active Trial Period.

Solicited Local AEs

Occurrence, intensity, and duration of solicited local AEs during the 8-day period after vaccination will be summarized for each group. Note, solicited local AEs are always assumed to be related to vaccination so no summaries based on causality will be performed.

Injection site erythema, swelling and induration will be measured using a provided ruler and the maximum diameter will be recorded for each day on the memory aid. The intensity for these symptoms will be graded as follows:

Table 3 Solicited Local Event Grading

MedDRA coded Preferred Term	Grade	Intensity
Injection site erythema, swelling, and induration	0	0
	1	< 30 mm
	2	≥ 30 – < 100 mm
	3	≥ 100 mm
Injection site pruritus	0	Absent
	1	Mild
	2	Moderate
	3	Severe
Injection site pain	0	Absent
	1	Painful on touch
	2	Painful when limb is moved
	3	Spontaneously painful/prevents normal activity

Solicited General AEs

Occurrence, relationship, intensity, and duration of solicited general AEs during the 8-day period after each vaccination will be summarized for each group based on the grades defined below:

Table 4 Solicited General Event Grading

MedDRA coded Preferred Term	Grade	Intensity
Body temperature*	0	< 37.5°C (< 99.5°F)
	1	≥ 37.5 – < 38.0°C (≥ 99.5 – < 100.4°F)
	2	≥ 38.0 – < 39.0°C (≥ 100.4 – < 102.2°F)
	3	≥ 39.0 – < 40.0°C (≥ 102.2 – < 104.0°F)
	4	≥ 40.0°C (≥ 104.0°F)
Headache, Myalgia, Nausea, Chills and Fatigue	0	None

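### The SAP's 'within 29 days' adverse event rows run to each subject's end-of-active-phase visit, not over the fixed 29 days that the endpoints state

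*SAP*

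**What the plan says.** **Endpoints.** Protocol 1.3 lists two 29-day safety endpoints. One is "Subjects reporting any SAE or AESI, regardless of relationship, within 29 days after vaccination". The other concerns related events of Grade 3 or higher. SAP 1.1 carries both over as supportive endpoints, the second as "Subjects reporting any Grade 3 or higher AEs assessed as related to trial vaccine within 29 days after vaccination". Protocol 9.18 names 8 and 29 days side by side as reporting windows after the first or second vaccination.

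**Derivation.** In SAP 4.5.2.2 a footnote is attached to the 29-day rows of both table lists. It begins "Within 29 days summaries includes through the day prior to second vaccination for Group 1 Vaccination Period 1" and otherwise runs the window "from the last/single booster vaccination through the end of the Active Trial Period for all groups". It adds: "The window for the end of the Active Trial Period visit is 28-35 days post last/single booster vaccination". The 8-day rows carry no footnote.

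**End of the period.** SAP 4.1.3 describes the safety analyses for the Active Trial Period as "accounting for any observations between the first vaccination and the EAP visit, inclusive of the EAP visit". For subjects who leave early, it takes results through 35 days after the last vaccination. The period definition in the same section also says that "any safety information collected within 35 days of their vaccination received will be included in summaries of the Active Trial Period".

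**Related places.** SAP 4.3.1.4 repeats the secondary analysis over 29 days after any vaccination, for related SAEs or AESIs and for related Grade 3 or higher events. It has neither the footnote nor a day rule. SAP 4.7 lists two changes to the protocol-planned analyses, and this is not one of them.

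**The concern.** The endpoint is a fixed window, but the derivation ends at a visit with a week of scheduling tolerance. The time over which a subject can contribute an event then depends on when the visit was booked, so the figure printed under the 29-day label is not a 29-day proportion.

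Two consequences follow within the SAP itself:

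- In the system organ class tables, which are themselves for the Active Trial Period, the 29-day sub-row for Groups 2 and 3 covers the same interval as its parent row. The sub-row adds no information, and the protocol endpoint is not isolated.
- A programmer could apply a true 29-day filter in SAP 4.3.1.4 and the EAP rule in SAP 4.5.2.2. That would report two different counts for one endpoint. The endpoint on SAEs or AESIs regardless of relationship has a stated window only under the footnoted rule, because SAP 4.3.1.4 covers related events.

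**Working it through.** The documents give no figure to reproduce for this point. The check is a day count.

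**Inputs**
- Day convention: SAP 4.5.2.1 describes the solicited period as "Days 1 to 8 following vaccination, 8-day period", starting on the day of vaccination. So 8 days are offsets +0 to +7. By the same convention, 29 days are offsets +0 to +28.
- EAP visit: +28 to +35 days after the last or single vaccination (SAP 4.5.2.2 footnote; SAP Appendices 2 and 3).
- Second vaccination in Group 1 (V4): V1 +28 to +35 days (SAP Appendix 2). The day before is +27 to +34.
- Early discontinuation: through +35 days (SAP 4.1.3).

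**Formula.** Window length = last eligible offset + 1. Excess = window length − 29.

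| Situation | Last offset | Window (days) | Excess over 29 | Ratio to 29 |
|---|---|---|---|---|
| Last or single vaccination | +28 to +35 | 29 to 36 | 0 to +7 | 1.00 to 1.24 |
| Group 1 Period 1 | +27 to +34 | 28 to 35 | −1 to +6 | 0.97 to 1.21 |
| Early discontinuation | +35 | 36 | +7 | 1.24 |

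The spread between subjects with in-window visits is 35 − 28 = 7 days after the last or single vaccination, and 34 − 27 = 7 days in Period 1. A subject who discontinues early can have a 36-day window, while a subject who completes with an EAP visit at +28 has 29.

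**Other day count.** If the vaccination day is not counted, the lengths are 28 to 35 days (−1 to +6 against 29) after the last or single vaccination, and 27 to 34 days (−2 to +5) in Period 1. The 7-day spread is unchanged.

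**What this could do to a proportion.** The documents give no event rates, so the 29-day incidence p is an assumption. With a constant hazard and every subject observed for 36 days, the proportion becomes 1 − (1 − p)^(36/29):

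| Assumed p over 29 days | At most, over 36 days |
|---|---|
| 1% | 1.24% |
| 5% | 6.17% |
| 10% | 12.3% |
| 20% | 24.2% |

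At p = 5% and n = 90, this is 90 × 0.05 = 4.5 subjects against at most 90 × 0.0617 = 5.6.

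**The case against.** The rule is disclosed. The footnote states it, with the 28 to 35 day range, below each affected table list. It follows the protocol's own definition of the active trial phase, it keeps events rather than dropping them, and all AEs are listed by onset date, so a strict 29-day count could be recovered. No hypothesis test is planned. All of this stands, and it makes the point minor. It does not turn a count up to a visit into the stated endpoint.

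A reader might infer that the 29-day counts are overstated. The documents support only that they may be. A visit at +28 gives exactly 29 days, and Group 1 Period 1 can be one day short. The 24% is a ceiling that needs every subject at +35. Turning it into event counts also needs a constant hazard, which suits events judged related to the vaccine poorly, because the time since dosing enters the causality assessment (Protocol 8.12).

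A reader might also infer a bias between doses because Group 3 was enrolled after Group 2. The documents do not support this. Both groups follow one schedule with the same EAP window, and nothing suggests that visits fell at different offsets.

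The 35-day sentence in SAP 4.1.3 could be read as one common cut-off for all subjects. That would remove the variation for SAEs and AESIs, which are collected beyond EAP, but the cut-off would still not be Day 29. Other unsolicited events are collected only through each subject's EAP visit.

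**Conclusion.** The point holds as a mismatch between the stated endpoint and its derivation. As written, the SAP's rule does not produce the 29-day endpoints of Protocol 1.3 and SAP 1.1, and the departure is not recorded in SAP 4.7.

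Counting the vaccination day as Day 1 and assuming in-window visits, the figures may include up to 7 extra days after the last or single vaccination, at most about 24% more observation time. Group 1 Period 1 ranges from 1 day short to 6 days long, at most about 21% more. Visits outside the window could widen this. The numerical effect is likely small, and smaller still for events that cluster soon after vaccination. No conclusion of the trial rests on it.

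**What to change.** In SAP 4.5.2.2 and 4.3.1.4, define the 29-day window by onset date: Day 1 (vaccination) to Day 29 after the relevant vaccination. For Group 1 dose 1, truncate at the second vaccination and state that this may leave 28 days when V4 falls at +28. Report later events only in the Active Trial Period tables. Add a rule for incomplete onset dates, since SAP 4.1.3 assigns these only to a study period. Counting an event as inside the window unless its date shows otherwise would match the worst-case principle of that section.

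The cost is a revised footnote, one sentence in SAP 4.3.1.4 and one date filter. No new data are needed: after the last vaccination an in-window EAP visit falls on Day 29 or later, so collection already covers the full window. Merely relabelling the rows as running to EAP would remove the conflict in the label, but it would need an entry in SAP 4.7 and would leave the protocol's endpoint unreported in those tables.
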